4.5 Exploratory Endpoints

Exploratory endpoints include the following:

- Quantitative measurements of fibrosis and fat on biopsy
 - Assessment of NASH CRN Fibrosis Score at Week 24
 - Proportion of participants with >=2 stage improvement
 - Changes in Fibrosis (as expressed by Shift from baseline)
 - Proportion of participants with >=1 stage improvement, no change, or worsening
 - Assessment of Ishak Fibrosis Score at Week 24
 - Proportion of participants with >=2 stage improvement
 - Changes in Fibrosis (as expressed by Shift from baseline)
 - Proportion of participants with >=1 stage improvement, no change, or worsening
 - Assessment of Fibrosis and NASH using digital pathology at Week 24
 - Absolute, percent change, and change from baseline
 - Assessment of CPA at Week 24
 - Proportion of participants with any improvement
 - Absolute, percent change, and change from baseline
 - Assessment of fat in stained tissue by morphometry and alpha smooth muscle actin (SMA) at Week 24
 - Absolute, percent change, and change from baseline
- Assessment of NAS score at Week 24
 - Changes in NAS (as expressed by shift from baseline, for each individual NAS components (Steatosis, inflammation, Ballooning) as well as Total score)

Sponsor: Bristol-Myers Squibb

[figure not shown]
Protocol no: MB130-068

- Proportion of participants with improvement, no change, or worsening in NAS Total
- Assessment of NASH using digital pathology
 - Absolute, percent change, and change from baseline
- Hepatic fat fraction as measured using MRI-PDFF at Week 24 and Week 48
 - Absolute, percent change, and change from baseline
 - Proportion of subjects in each treatment group with $\geq 30\%$ relative reduction, $\geq 20\%$ relative reduction, $\geq 10\%$ relative reduction, and $\geq 5\%$ absolute reduction
- Noninvasive measures of fibrosis and/or cirrhosis
 - Liver stiffness as determined by Magnetic Resonance Elastography (MRE) at Week 24 and Week 48
 - Absolute, percent change, and change from baseline
 - Proportion of subjects in each treatment group with $\geq 19\%$ or $\geq 15\%$ reduction
- Noninvasive scores of hepatic fibrosis (AST-Platelet Ratio Index (APRI), Fibrosis 4 (FIB-4), Enhanced Liver Fibrosis (ELF), and NAFLD Fibrosis Score) from Day 1 to Week 24 and Week 48
 - Absolute, percent change, and change from baseline
 - Proportion of participants in each ELF category by time point
- Metabolic assessments at Week 24 and Week 48

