 - Physical assessments (body weight, waist circumference, and body mass index (BMI)) by time point
 - Serum lipids (low-density lipoprotein (LDL), high-density lipoprotein (HDL), and triglycerides (TGs))
 - Absolute and change from baseline
 - Abnormal post-baseline values according to thresholds identified in SAP Section 4.3.5
 - Plasma glucose, Plasma insulin, Hemoglobin A1c
 - Absolute and change from baseline
 - Abnormal post-baseline values according to thresholds identified in SAP Section 4.3.5
- Patient-reported outcomes at Week 24 and Week 48
 - 3-Level EuroQol of Life 5 Dimension (EQ-5D-3L) Questionnaire
 - Absolute and change from baseline in visual analog score and utility index
 - Proportion of participants in each 3-level dimension by time point
 - 36-Question Short Form Quality-of-Life (SF-36) Questionnaire
 - Absolute and change from baseline in continuous variables defined in SAP Section 8.0
 - Chronic Liver Disease Questionnaire-Nonalcoholic Fatty Liver Disease (CDLQ-NAFLD)
 - Absolute and change from baseline in continuous variables defined in SAP Section 8.0
- Exploratory biomarkers
 - Transaminases
 - ALT normalization ($ALT \leq ULN$) at Week 24 and Week 48
 - AST normalization ($AST \leq ULN$) at Week 24 and Week 48
 - ALT at each visit through Week 52/PTFU
 - AST at each visit through Week 52/PTFU
 - Change from Baseline (Day 1 predose) ALT levels at each visit through Week 52/PTFU Visit
 - Change from Baseline (Day 1 predose) AST levels at each visit through Week 52/PTFU Visit.
 - PRO-C3 (N-terminal type 3 collagen propeptide)

[figure not shown]
Sponsor: Bristol-Myers Squibb

Protocol no: MB130-068

- Assessment of PRO-C3 levels at each visit through Week 52/PTFU
- Change from Baseline (Day 1 predose) in PRO-C3 levels at each visit through Week 52/PTFU Visit

- Assessment of adiponectin at each visit through Week 52/PTFU
 - Absolute, percent change, and change from baseline

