6.4 Exploratory Analyses

Analyses for exploratory endpoints will be performed using the mITT or safety populations.

Exploratory dichotomous response variables will be summarized in a manner similar to that used for the secondary efficacy analyses. In addition, summaries of ≥ 1 stage improvement, no change, and worsening will be tabulated and graphically presented for NASH CRN Fibrosis Score, Ishak Fibrosis Score, and NAS Total at Week 24. For these analyses, participants without a Week 24 or ET result will be classified into the "Worse" category for these exploratory summaries.

Early termination visits for non-biopsy endpoints such as imaging and biomarkers may occur at other time points and will not be summarized together with Week 24. For non-biopsy endpoints, ET will be summarized separately in the summary tables. Imputation on missing data will not be performed for non-biopsy endpoints.

Summary statistics will be tabulated for all treated subjects by treatment and by Visit. Continuous data will be summarized using n, mean, standard deviation, median, minimum, and maximum.

Analysis of covariance (ANCOVA) model will be used to explore change from baseline for endpoints having a baseline and a post-baseline values.

Repeated measures analysis will model the change from baseline for the endpoint in presence of repeated measurements taken at various timepoints on/before the analysis visit.

Sponsor: Bristol-Myers Squibb

Protocol no: MB130-068

The model will include treatment group, visit, baseline value, treatment * visit and baseline stratification factors as main effects. An unstructured covariance matrix will be used to represent the correlation of the repeated measures within each subject. The model will provide point estimates, standard errors and 2-sided 95% confidence intervals for mean change from baseline at by time points.

Other biomarkers will be descriptively summarized by time point and will include percent change from baseline in addition to change from baseline. Exploratory endpoints assessing relationships will be graphically presented.

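### The exploratory repeated-measures model has no baseline-by-visit term; if the slope on baseline changes over 48 weeks, Week 48 estimates for the frequently sampled biomarkers lose some precision

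*SAP*

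**What the plan says.** SAP 6.4 describes a repeated-measures model for exploratory endpoints: "Repeated measures analysis will model the change from baseline for the endpoint in presence of repeated measurements taken at various timepoints", limited to measurements up to the visit being analysed. Its terms are: "The model will include treatment group, visit, baseline value, treatment * visit and baseline stratification factors as main effects". The covariance is flexible: "An unstructured covariance matrix will be used to represent the correlation of the repeated measures within each subject". Its stated output is: "The model will provide point estimates, standard errors and 2-sided 95% confidence intervals for mean change from baseline at by time points". No other section of the SAP or protocol adds a baseline-by-visit term.

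The same section plans a second model: "Analysis of covariance (ANCOVA) model will be used to explore change from baseline for endpoints having a baseline and a post-baseline values". It also rules out imputation: "Imputation on missing data will not be performed for non-biopsy endpoints".

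The visit patterns differ by endpoint:

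- **PRO-C3 and adiponectin:** Weeks 4, 8, 12, 24 and 48, then Week 52 (Protocol 8.5.1). SAP 4.5 lists, for example, "Change from Baseline (Day 1 predose) in PRO-C3 levels at each visit through Week 52/PTFU Visit".
- **ALT and AST:** every visit.
- **Imaging and most other continuous endpoints:** two post-baseline visits, for example "Hepatic fat fraction as measured using MRI-PDFF at Week 24 and Week 48". MRE, ELF, the metabolic measures and the patient-reported outcomes follow the same two visits.

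**The concern.** The model lets the treatment effect vary by visit and, through the unstructured covariance, lets the residual variances and correlations vary too. Only the covariate effects are held constant. For a biomarker sampled from Week 4 to Week 48, one slope is right only if the regression on baseline is the same at both ends. A value taken four weeks after baseline would usually follow baseline more closely than one taken 48 weeks after. With four of the five PRO-C3 visits at or before Week 24, the common slope is set mainly by early data, and the misfit at Week 48 goes into residual variance. The unstructured covariance absorbs that misfit but does not remove it.

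Week 48 matters because the only scheduled on-treatment biopsy is at Week 24. Efficacy evidence at the end of treatment therefore comes from the exploratory endpoints, and Protocol 6.2.1 says that Phase 3 design and dose selection will draw on all the analyses together. With no imputation for these endpoints, the repeated-measures model also carries whatever handling of missing data there is.

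**Working it through.** **Plan's own figure.** There is none to reproduce. The documents give no SD, correlation, power or precision figure for this model. The only power statement concerns the primary trend test and does not bear on this point.

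**Inputs from the documents.** Model terms and covariance (SAP 6.4); visit schedules (SAP 4.5, Protocol 8.5.1); 197 randomised, about 49 per arm (Protocol 6.2).

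**Inputs assumed.** Baseline variance 1 and equal SDs at all visits. Correlation between two measurements t weeks apart is k·exp(−λt), with k = 0.8 or 0.9 and λ = 0.005 to 0.02 per week. Write r_t for the correlation of visit t with baseline.

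**Formulas (large sample, complete data).**

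1. The slope of change on baseline at visit t is β_t = r_t − 1.
2. The conditional covariance of the visits given baseline is S = R − rr′, so at Week 48 it is S₄₈ = 1 − r₄₈².
3. The common-slope model converges to b = (1′S\*⁻¹β)/(1′S\*⁻¹1), with S\* = S + (β − b)(β − b)′, solved by iteration.
4. The Week 48 variance excess over a model with its own slope at each visit is (β₄₈ − b)²/S₄₈.

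**Results.**

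| Visits | k, λ | r at Week 4 | r at Week 48 | b | β₄₈ | S₄₈ | Excess |
|---|---|---|---|---|---|---|---|
| 4, 8, 12, 24, 48 | 0.8, 0.005 | 0.78 | 0.63 | −0.256 | −0.371 | 0.604 | 2.2% |
| same | 0.8, 0.01 | 0.77 | 0.50 | −0.302 | −0.505 | 0.755 | 5.5% |
| same | 0.8, 0.02 | 0.74 | 0.31 | −0.387 | −0.694 | 0.906 | 10.4% |
| same | 0.9, 0.01 | 0.86 | 0.56 | −0.192 | −0.443 | 0.690 | 9.2% |
| same | 0.9, 0.02 | 0.83 | 0.34 | −0.277 | −0.655 | 0.881 | 16.3% |
| 24, 48 | 0.8, 0.005 | – | 0.63 | −0.323 | −0.371 | 0.604 | 0.4% |
| 24, 48 | 0.9, 0.02 | – | 0.34 | −0.525 | −0.655 | 0.881 | 1.9% |

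Example, fifth row: (−0.655 + 0.277)²/0.881 = 0.143/0.881, about 16%. In standard-error terms √1.163 = 1.078, about 8%.

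The nine on-treatment ALT/AST visits give 2.1% to 16.0% on the same grid. With λ = 0 the slopes are equal and the excess is 0% for every schedule.

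**Other assumed shapes.** With correlation falling in a straight line to Week 48 (0.8 to 0.6, 0.8 to 0.5, 0.85 to 0.4), the excess is:

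- PRO-C3/adiponectin: 3.0%, 6.0%, 13.2%
- ALT/AST: 2.9%, 5.8%, 13.0%
- two-visit endpoints: 0.6%, 1.2%, 2.7%

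The equal-SD assumption matters. If the SD falls to 0.7 of baseline by Week 48 and correlation follows 0.9·exp(−t/48), the excess is about 30% with five visits and 2.3% with two. If the SD grows to 1.3 with the 0.8 to 0.5 line, it is 1.3% and 0.4%.

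**Simulation checks (49 per arm).** Fitting both models to complete data, the empirical SDs of a Week 48 arm difference were 0.1912 (common slope) and 0.1794 (baseline by visit) with five visits and 0.85 falling to 0.4. The variance ratio is (0.1912/0.1794)² = 1.136, against 1.132 from the formula. With two visits and 0.8 falling to 0.5, the SDs were 0.1685 and 0.1667, ratio 1.022 against 1.012. Both models were unbiased within simulation error. A separate simulation of three five-visit settings from the grid gave 1.036, 1.073 and 1.137, against 1.055, 1.092 and 1.163 by formula, so the formula can slightly overstate the loss at this sample size.

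**Dropout.** With an assumed 12% to 15% missing at Week 48, depending on baseline in one arm, the common-slope estimate differed from the interaction model by 0.0171 − 0.0019 = 0.015 SD (two visits) and 0.0378 − 0.0113 = 0.027 SD (five visits).

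**Price of the extra term when it is not needed.** With truly equal slopes (correlation 0.7, five visits), simulation put the loss at 0.1% to 0.4% of variance.

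**The case against.** A common baseline slope is a legitimate model, and nothing in the documents shows that the slopes differ. No correlation or SD is given for any exploratory endpoint, and if the slopes are equal nothing is lost. This stands, and it is why the point is conditional.

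Most of the endpoints are measured only at Weeks 24 and 48, where there is no run of early visits to pull the slope. A variance excess of 0.4% to 3% is at most about 1.5% of a standard error. This also stands: the point carries practical weight only for PRO-C3, adiponectin and the transaminases.

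The Week 48 evidence does not depend on this model alone. SAP 6.4 also plans an ANCOVA, by-visit descriptive summaries and analyses of dichotomous responses, and SAP 4.5 includes Week 48 responder measures for MRI-PDFF, MRE and ALT/AST normalisation. The stated output of the repeated-measures model is mean change by time point; contrasts between arms can be derived from it but are not specified. All true. The ANCOVA does not settle the matter, however. The SAP does not say whether it is fitted visit by visit. If it is, two planned models adjust the same Week 48 data with different slopes, and the SAP does not say which is to be reported.

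A reader might infer that the off-drug Week 52 visit also distorts the Week 48 slope. It does not, because each fit uses only measurements up to its own analysis visit.

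**Conclusion.** The baseline-by-visit term is absent, and its absence can only cost precision in large samples. Under the assumed correlations the cost at Week 48 is about 2% to 16% of variance for PRO-C3, adiponectin and ALT/AST, about 0.4% to 3% for two-visit endpoints, and zero if the slopes are equal. Shrinking SDs could push the first range higher, and growing SDs would bring it down.

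Three stronger readings are tempting and not supported:

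- **That the Week 48 adjustment is certainly wrong.** This needs correlations that the documents do not give.
- **That the trial as a whole loses the equivalent of some 27 participants.** That is 197 × (1 − 1/1.163), the most extreme setting on the grid, and it applies to frequently sampled biomarkers only.
- **That the treatment comparisons are biased.** With complete data they are not. Baseline-dependent dropout could add a shift of about 0.02 to 0.03 SD under the dropout assumed here.

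The analysis is exploratory, and the primary and secondary biopsy endpoints are untouched. This is a minor, inexpensive improvement. It is worth making because the loss from omitting the term when it is needed is larger than the loss from including it when it is not.

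**What to change.** In SAP 6.4, add baseline value * visit to the repeated-measures model for every endpoint with more than one post-baseline visit, and leave the rest of the model unchanged.

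The cost is one degree of freedom per additional visit. In a Week 48 analysis that is 1 for the two-visit endpoints, 4 for PRO-C3 and adiponectin (five visits) and 8 for ALT/AST (nine visits), each one more where Week 52 is itself the analysis visit for an endpoint measured then. With about 197 participants this is negligible. No data collection or timing changes.

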6.5 General Methodology

All analyses will use SAS® version 9.4 or higher.

- Descriptive summaries will be tabulated by treatment group and overall, unless otherwise specified.
- Categorical data will be presented using counts and percentages, with the number of participants in each category as the denominator for percentages
 - For by-visit summaries denominators may be adjusted to reflect the number of participants in the study at the time of the visit
 - Percentages will be rounded to one decimal place except 0% and 100% which will be displayed without any decimal places and percentages will not be displayed for zero counts.
- Continuous data will be summarized using the number of observations (n), mean, SD, median, first quartile, third quartile, minimum, and maximum. Minimum and maximum will be rounded to the precision of the original value.
 - Mean, median, first and third quartiles will be rounded to 1 decimal place greater than the precision of the original value. The SD will be rounded to 2 decimal places greater than the precision of the original value, with the original value having up to a maximum of 3 decimal places.
- P-values will be presented to 3 decimal places.

6.5.1 Participant Disposition

The number and percentage of participants in each analysis population will be presented. The number and percentage of participants randomized but not treated will be included.

The number of participants randomized will be presented by treatment group, along with the number and percentage of participants who completed, discontinued, and are ongoing treatment or the study at the time of the data cut by treatment group.

Enrollment by country and center will be tabulated among randomized participants.

Also, by-participant listings will be generated.

6.5.2 Demographics and Baseline Disease Characteristics

Demographics and baseline disease characteristics will be summarized by treatment group and overall for the mITT population. Individual participant listings will be provided to support the summary tables.

6.5.3 Medical History

A summary of general medical history will be presented by Medical Dictionary for Regulatory Activities (MedDRA) Version 20.1 or higher SOC and PT for the safety population. The number and percentage of participants with each event will be presented by SOC and PT. Note that counting will be by participant not event and participants are only counted once within each SOC and PT.

Sponsor: Bristol-Myers Squibb

Protocol no: MB130-068

A separate specific disease history table, including history of prior NASH therapy and history of Hepatitis C Virus, will be provided by treatment group and total for the safety population. The proportion of participants with each type of disease history condition (eg history of Type 1 Diabetes, History of Type 2 Diabetes, etc.) will be included. These histories will be presented in participant listings.

Data collected on prior surgeries will be listed.

6.5.4 Prior Medications

Prior medications are defined as medications taken prior to the first dose of study medication and discontinued before the first dose of study medication.

Prior medications summaries will be presented for the safety population by treatment group and overall. A summary showing the number and percentage of participants who had prior medications will be presented by World Health Organization (WHO) Anatomic Therapeutic Classification (ATC) level and preferred name, version WHO DD 2017 SEP01 DDE+HD or higher. Note that counting will be by participant and participants are only counted once within each ATC and PT.

6.5.5 Protocol Deviations

Important protocol deviations will be summarized by number and percentage of participants experiencing each deviation category. All protocol deviations will be listed and will indicate if the deviation was COVID 19 related.

6.5.6 Treatments

6.5.6.1 Extent of Study Treatment Exposure

Summary statistics for study exposure will be based on the safety population and presented by treatment group and pooled BMS-986036.

The following summaries will be included:

- Number of participants receiving at least 1 injection
- Number of participants with at least 1 missed exposure visit and reason
- Number of participants with at least 1 dose not taken as planned and reason
- Frequency of the number of weeks of treatment (eg 16 weeks, 20 weeks, etc.)
- Continuous summary of treatment duration (in weeks)
- Summary of percentage of treatment completed

Participant listings will present exposure data at the injection-level. End of treatment reasons will be listed separately, as well as device malfunctions.

6.5.6.2 Concomitant and Follow-up Medications

Concomitant medications are defined as any medication started before/on/after the first dose of study medication until the Week 52/PTFU Visit,

Concomitant medications (through Week 52 / PTFU), bone-density related medications and NASH therapies taken after the end of study treatment (Week 52/PTFU through 6-month Follow-up) will be presented separately among the safety population by treatment group and overall. The summaries will include the number and percentage of participants who had medications and will be presented by WHO ATC drug name and preferred name, version WHO-DD March 2015 or later.

A participant listing of prior, concomitant and follow-up medications will be provided to support the tables.

Sponsor: Bristol-Myers Squibb
Protocol no: MB130-068

6.5.6.3 Diagnostic and Medical Procedures

Diagnostic and medical procedures will be presented in a participant listing.

7.0 Sequence of Planned Analyses

Locking, freezing, cleaning, and details for transferring of data will be described in a separate study plan.

7.1 Interim Analysis

After approximately 100 participants have had their Week 24 biopsy assessments, an interim analysis may be performed for the purpose of internal decision making for future clinical development. Analyses will be completed by pre-specified unblinded individuals.

If BMS elects to perform this analysis, the SAP will be modified accordingly and will provide the details regarding the selected analyses.

7.2 Week 24 Data Analysis

Due to COVID-19 the Week 24 data analysis is based on approximately 160 subjects when planned sample size was reached which occurred at eCRF data cut-off date of May 29 2020. The study will continue to enroll for Week 52 data analysis in a blinded fashion as planned for 197 patients. The level of unblinding and roles to be unblinded will be specified in a separate unblinding study plan that will be finalized prior to the database lock (reference for unblinding plan). The study will continue in a blinded fashion following this analysis. Study data through Week 24 will be analyzed by pre-specified unblinded individuals as specified in the unblinded plan.

- All Efficacy data will be summarized based on mITT principle for DB Lock defined by eCRF date cut-off MAY 29, 2020 on all participants who have completed liver biopsy.
- If the biopsies were delayed and performed between Week 24 and Week 48, the biopsies results will be included in the planned Week 24.
- Safety data will be summarized using Safety population through DB lock defined by eCRF date cut-off May 29, 2020.
- All available data beyond Week 24 will be summarized descriptively.
- SAS datasets and subject level data listings will be shared in accordance with unblinding plan (add reference)

This analysis will include the primary and secondary efficacy endpoints, and selected safety, PK, and exploratory endpoints. The list of tables, figures, and listings (TFLs) to be provided for this analysis will be kept in a separate document outside the SAP.

